6.1.3. Time to event endpoints

- **OS**

OS is defined as the time from date of the first dose of any of the study medications to date of death due to any cause. Patients last known to be alive will be censored at the date of last contact. OS will be summarized in months:

OS (months) = [date of death or censoring–date of the first dose +1]/30.4375.

- **Duration of complete response (DoCR)**

DoCR is only defined in MDS patients or AML patients achieving a CR in the expansion component. DoCR is defined as the duration from date of first achieving CR to the date of disease progression (relapse) after CR, or death due to any cause. Patients last known to be alive who are free from disease progression or relapse after CR are censored at the date of the last assessment that verifies their disease status. The minimum DoCR is 4 weeks by definition (CR must last at least 4 weeks to qualify as such per IWG 2006) for MDS patients.

- **Duration of response (CR+PR)**

Duration of Response (DoR) (including CR+PR) is defined for patients in Safety LIC and the expansion cohort who have ever achieved CR or PR on study as the time from date of first achieving CR or PR to the date of disease progression, or relapse after CR/PR, or death due to any cause. Patients last known to be alive who are free from disease progression or relapse after CR/PR are censored at the date of last disease assessment that verifies their status. Note that minimum DoR is 4 weeks by definition (CR/PR must last at least 4 weeks to qualify as such per IWG 2006) for MDS patients.

- **CCI**

[REDACTED]

- **Time to Response (CR)**

Time to response (TTR) is only defined for patients in the expansion component of the study who have ever achieved CR on study as the time from date of the first dose of study drug to date of the first documentation of response (CR). Note that response needs to be confirmed by definition (CR must last at least 4 weeks to qualify as such per IWG 2006) for MDS patients.

- **CCI**

[REDACTED]

CCI [REDACTED]

[REDACTED]

6.2. Safety Endpoints

Adverse Events:

Adverse Events (AEs) will be graded by the investigator according to the Common Terminology Criteria for Adverse Events (CTCAE) version 4.03 and coded using the Medical Dictionary for Regulatory Activities (MedDRA). For other AEs without specific CTC definitions, results are identified according to CTCAE “other” categories. Adverse events will be assigned to the appropriate cycle based on Day 1 of each cycle. Specifically, treatment emergent and treatment related AEs are defined as follows.

Treatment Emergent Adverse Events

- All deaths from start of treatment until 28 days after the final dose.
- All treatment related SAEs even if occurring after 28 days after the final dose or after EOT.
- All treatment unrelated SAEs from treatment start until 28 days after final dose of treatment.
- All treatment Non-fatal AEs occurring after treatment start up until 28 days after final dose of treatment.
- Disease progression is not considered a treatment emergent adverse event unless the subject dies of disease prior to 28 days after discontinuation of treatment.
- Events that are continuations of baseline abnormalities are considered treatment emergent adverse events only if there is an increase in grade over baseline.

Treatment Related Adverse Events

Treatment Related Adverse Events are treatment emergent adverse events with cause categorized by the investigator as related to study treatment. Events that are continuations of baseline abnormalities (signs and symptoms) are not considered treatment emergent, and therefore not considered treatment related, unless there is an increase in grade over baseline.

Laboratory Test Abnormalities:

7.2. Efficacy Analysis

For primary and secondary efficacy analyses, no values will be imputed for missing data. Censoring for time-to-event endpoints are defined in [Section 6.1](#). In the assessment of response (at interim or final analysis), patients who are not known to have achieved response will be counted as non-responders.

7.3. Pharmacokinetics

Concentrations below the limit of quantification

In all data presentations (except listings), concentrations below the limit of quantification (BLQ) will be set to zero. (In listings BLQ values will be reported as “<LLQ”, where LLQ will be replaced with the value for the lower limit of quantification).

Deviations, missing concentrations and anomalous values

In summary tables and plots of median profiles, statistics will be calculated with concentrations set to missing if one of the following cases is true:

1. A concentration has been reported as ND (i.e., not done) or NS (i.e., no sample),
2. A deviation in sampling time is of sufficient concern or a concentration has been flagged anomalous by the pharmacokineticist.

Note that summary statistics will not be presented at a particular time point if more than 50% of the data are missing.

Pharmacokinetic parameters

Actual PK sampling times will be used in the derivation of PK parameters.

If a PK parameter cannot be derived from a subject’s concentration data, the parameter will be coded as NC (i.e., not calculated). (Note that NC values will not be generated beyond the day that a subject discontinues).

For evaluation of changes in pharmacokinetics of a compound when administered alone vs. in combination, only subjects with matching pair of pharmacokinetic assessments under both conditions will be included in the pharmacokinetic summary (i.e., alone and in combination).

In summary tables, statistics will not be presented for a particular treatment group if more than 50% of the data are NC. For statistical analyses (i.e., analysis of variance), PK parameters coded as NC will also be set to missing.

If an individual subject has a known biased estimate of a PK parameter (due for example to an unexpected event such as vomiting before all drug is absorbed in the body), this will be footnoted in summary tables and will not be included in the calculation of summary statistics or statistical analyses.

[figure not shown]
7.4. QTc

For analyses using the QTc analysis set, no values will be imputed for missing data except for averaging of triplicate measurements. If one or two of the triplicate measurements for an ECG parameter are missing, the average of the remaining two measurements or the single measurement can be used in the analyses. If all triplicate measurements are missing at a time point for an ECG parameter, no values will be imputed for this time point and no analyses related to this time point will be performed. Unplanned ECGs will be in triplicate and averaged.

7.5. Pharmacodynamic Parameters

Missing data for the pharmacodynamic parameters will be treated as such and no imputed values will be derived.

CCI

8. STATISTICAL METHODOLOGY AND STATISTICAL ANALYSES

8.1. Statistical Methods

Efficacy analyses will use the FAS. They will be reported for the safety LIC, the expansion MDS cohort, and expansion AML cohort separately. Safety analyses will be reported separately for the safety LIC and each cohort in the expansion, as well as all three cohorts pooled.

8.1.1. Analyses for Binary Endpoints

The rates of binary endpoints will be provided along with the corresponding two-sided 95% confidence intervals using exact method unless otherwise stated.

8.1.2. Analyses for Time-to-Event Data

Unless otherwise stated, time-to-event endpoints will be summarized using the Kaplan-Meier method and displayed graphically (with number of patients still at risk noted on the horizontal axis) when appropriate.

Median event times and two-sided 95% confidence intervals for each time-to-event endpoint will be provided. Point estimate of selected survival probabilities and two-sided 95% confidence intervals will also be provided, where the log-log transformation and back-transformation will be used in the calculation.

8.1.3. Analyses for Continuous Data

Descriptive statistics, such as the mean, standard deviation, coefficient of variation, median, minimum, and maximum values, will be provided for continuous endpoints. Biomarker and PK summaries will also include coefficient of variation percent (%CV).

8.2. Statistical Analyses

8.2.1. Analysis of Primary Endpoints

Analysis of Primary Endpoint of Safety LIC

The primary endpoint of safety LIC of the study is safety and is detailed in [Section 8.2.3.1](#).

Analysis of Primary Endpoint of the Expansion Component

The proportion of patients achieving CR is the primary endpoint for the expansion cohorts.

A confirmation of response (peripheral blood only) is required 4 weeks after the first assessment per IWG 2006 for MDS patients. The final analyses for MDS cohorts will be performed after all patients in the expansion MDS cohort have been followed for at least 28 weeks (to allow for confirmation of response per IWG 2006). No confirmation is needed for the expansion AML cohort. The final analyses for the AML cohort will be performed after all patients in this cohort have been followed for at least 24 weeks.

The proportion and two-sided 95% CI (using exact method) of patients achieving CR will be provided at the time of the final analysis based on the FAS for MDS cohort and AML cohort separately.

8.2.2. Analysis of Secondary Endpoints

8.2.2.1. Analysis of Secondary Endpoints of Safety LIC

8.2.2.1.1. Response Rate (RR)

Response rate (CR+PR) is a secondary endpoint for the safety LIC. A confirmation of response (Peripheral Blood only) is required 4 weeks after the first assessment per IWG 2006. The final analyses will be conducted after all patients in the safety LIC have been followed for 28 weeks (to allow for confirmation of response per IWG 2006).

The proportion and two-sided 95% CI (using exact method) of patients achieving response will be provided for the safety LIC.

8.2.2.1.2. Other Efficacy Measures

The proportion of patients ever achieving HI (MDS only), mCR, Cytogenetic Response (complete and partial), and SD will be estimated with two-sided 95% CI (using exact method) respectively for the safety LIC.

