An open-label expansion consisting of approximately 60 patients with previously untreated Intermediate, High, or Very High risk MDS per IPSS-R (n=30) and AML patients who are not candidates for intensive chemotherapy (n=30). Patients will receive glasdegib at a starting dose of 100 mg QD given orally in combination with azacitidine per local label or per the Investigational Product Manual (or Summary of Product Characteristics [SPC]). Azacitidine may be administered by SC injection or intravenous (IV) infusion at the starting dose of 75 mg/m²/day for 7 days every 28 days. Alternate dosing schedules to administer the 7 azacitidine doses to accommodate subject and treatment center availability are allowed. The primary objective of the expansion component of the study is to demonstrate that the CR rate of the combination treatment in each patient population is reasonably better than the historical CR rate for azacitidine alone using a Bayesian decision criterion allowing early stopping for futility. Analysis of specific safety criteria will also be performed to evaluate stopping enrollment for a specific cohort when the rate of pre-defined safety events of interest surpasses a pre-defined threshold.

Figure 1. Schematic of Study Design

*MDS patients enrolled in the safety lead-in component must have Intermediate-2 or High-Risk disease according to IPSS. MDS patients enrolled in the expansion component must have Intermediate, High, or Very High risk disease according to IPSS-R.

Study Assessments

Patients will be followed for efficacy throughout the study by means of bone marrow aspirates. Following study entry, bone marrow biopsies will only be required if adequate bone marrow aspirates are not obtained. A CR or PR needs to be confirmed at least 4 weeks after the bone marrow (BM) evaluation by assessing the stability of improved counts on peripheral blood (PB) according to the 2006 IWG criteria; an additional marrow confirmatory specimen is not required (applies to all patients in the safety LIC and only MDS patients in the expansion component).

Blood counts will be monitored for signs of hematologic improvement (HI) (applies to all patients in the safety LIC and only MDS patients in the expansion component).

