3.3.2. Study Assessments Summary

Patients will be followed for efficacy throughout the study by means of bone marrow aspirates. Following study entry, bone marrow biopsies will only be required if adequate bone marrow aspirates are not obtained. A CR or PR response needs to be confirmed at least 4 weeks following the BM evaluation by assessing the stability of improved counts on PB, an additional bone marrow confirmatory specimen is not required (applies to all patients in the safety LIC and only MDS patients in the expansion component).

CCI [REDACTED] Transfusional support (red blood cells and platelets) will also be recorded. Timely and complete (bone marrow AND peripheral blood counts) disease assessments at screening and during the study, whenever clinically indicated, are essential. Failure to perform any of the required disease assessments will result in the inability to determine disease status for that time point and may weaken the conclusions of the study.

Safety assessments (laboratory, instrumental and clinical) and PK assessments will be performed regularly during the active treatment period in both components of the study.

DDI assessments were performed in the safety LIC only.

CCI [REDACTED]

Please refer to the [Schedule of Activities for the Safety Lead-in Cohort](#) and the [Schedule of Activities for the Expansion: MDS and AML Patients](#) for a complete list of assessments to be performed on patients in the study.

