2.1.1. Safety Lead-In Cohort (LIC)

As of 23 September 2015, a safety LIC of 12 patients with previously untreated Intermediate-2 or High-Risk MDS per IPSS (n=7), AML with 20-30% blasts and multi-lineage dysplasia (n=3), erythroleukemia (n=1), and CMML (n=1) were enrolled and received open-label treatment with PF-04449913 at a starting dose of 100 mg given orally once/day in combination with azacitidine at the starting dose of 75 mg/m²/day given SC for 7 consecutive days every 28 days. An evaluation of the DDI potential between PF-04449913 and azacitidine was performed. An internal safety review team reviewed the LIC data after each patient had received at least 4 weeks of treatment and determined that the safety profile of PF-04449913 in combination with azacitidine in the defined population was consistent with what is expected for PF-04449913 or azacitidine alone with no unexpected toxicities identified, therefore the combination was deemed acceptable to proceed to the next phase of development.

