6.1.1. Response endpoint

- **CR rate**

Primary endpoint for the expansion component of the study is proportion of patients achieving CR. Of note a confirmation of response (Peripheral Blood only) is required 4 weeks after the first assessment per IWG 2006 for MDS patients.

- **Response Rate**

Response rate (percentage of patients achieving CR + PR) is defined by modified IWG criteria (2006) (Appendix 2).

Of note a confirmation of response (Peripheral Blood only) is required 4 weeks after the first assessment per IWG 2006 for MDS patients.

- CCI [REDACTED]

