6.1.2.1.2. MDS Cohort

Hematologic Responses

- CR
- PR,
- marrow CR (mCR)
- SD
- Complete or Partial Cytogenetic Response

Hematologic Improvement (HI):

HI (defined only for MDS patients) is derived based on hematology lab and RBC transfusion data according to criteria detailed in Appendix 2.

Of note that HI for neutrophils improvement obtained within 3 weeks of the last administration of growth factors (GCSF/GM-CSF) is considered not evaluable. Additionally, HI for erythroid improvement obtained within one week of the last administration of transfusion of red blood cell is considered not evaluable, and HI for platelets improvement obtained within 3 days of the last administration of transfusion of platelets is considered not evaluable.

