Neutrophil Response (pretreatment <1 x 10 ⁹ /L)*	At least a 100% increase and an absolute increase >0.5 x10 ⁹ /L
Progression or relapse after HI in the absence of another explanation	At least one of the following: 
 • At least 50% decrease from maximum response levels in granulocytes or platelets; • Reduction in Hgb by ≥1.5g/dL; • Transfusion dependence.

*Pretreatment counts averages of at least 2 measurements (not influenced by transfusions) ≥1 week apart.

** Hematologic Improvement must last ≥ 8 weeks and is derived based on lab data entered in the database.

***This criteria will be applied also to patients with oligoblastic AML and CMML without proliferative disorder.

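### SAP 8.2.2.1.2 limits lead-in hematologic improvement to MDS patients, leaving out 5 of the 12 patients whom the protocol includes

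*SAP*

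**What the plan says.** **HI in the SAP.** Section 8.2.2.1.2, which specifies the lead-in analysis, estimates "The proportion of patients ever achieving HI (MDS only), mCR, Cytogenetic Response (complete and partial), and SD", each with an exact 95% CI. Section 6.1.2.1.2, under the heading MDS Cohort, states that "HI (defined only for MDS patients) is derived based on hematology lab and RBC transfusion data". The footnote to the IWG tables in Appendix 2, which include the HI table, reads "This criteria will be applied also to patients with oligoblastic AML and CMML without proliferative disorder".

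**HI in the protocol.** The Summary, under Study Assessments, states: "Blood counts will be monitored for signs of hematologic improvement (HI) (applies to all patients in the safety LIC and only MDS patients". The limit to MDS at the end of that sentence refers to the expansion component. Section 2.2 lists HI among the lead-in secondary endpoints with no disease limit. Section 7.7.1 applies the IWG criteria to every lead-in patient and, in the expansion, to MDS patients. Section 9.3.6 names HI as a measure for the lead-in and for the expansion MDS cohort.

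**Confirmation of response.** SAP 6.1.1 notes that confirmation "is required 4 weeks after the first assessment per IWG 2006 for MDS patients". SAP 8.2.2.1.1, on the lead-in response rate, says "A confirmation of response (Peripheral Blood only) is required 4 weeks after the first assessment per IWG 2006", with no disease limit. Protocol 3.3.2 describes the scope of confirmation as "applies to all patients in the safety LIC and only MDS patients in the expansion component".

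**The concern.** The protocol draws its line between study components: HI for everyone in the lead-in, and for MDS patients alone in the expansion. SAP 8.2.2.1.2 applies the expansion limit to the lead-in. The restriction does not appear among the main changes in SAP section 1, and no reason is given for it.

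Two things are at stake. A protocol-defined secondary endpoint would go unreported for patients in whom it was meant to be assessed. And the text does not fix the denominator: efficacy analyses use the full analysis set (SAP 8.1), but a parenthesis limiting the measure to one disease can be read as limiting the denominator too. Two programmers could produce different tables from the same data.

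**Working it through.** **1. The plan's own figure.** Neither document gives an expected HI rate or precision for the lead-in. The only lead-in design figure is the chance of seeing at least one adverse event at 15% incidence with about 10 patients (protocol 9.1.1): 1 − 0.85^10 = 0.803, which reproduces the stated 80%. This point does not touch it.

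**2. Who is left out.** SAP 2.1.1 gives the disease mix: "High-Risk MDS per IPSS (n=7), AML with 20-30% blasts and multi-lineage dysplasia (n=3), erythroleukemia (n=1), and CMML (n=1) were enrolled". Non-MDS patients: 3 + 1 + 1 = 5; check 12 − 7 = 5; 5/12 = 41.7%. This keeps CMML apart from MDS, as both documents do when describing the lead-in. If CMML were grouped with MDS, as protocol 4.1.2 does for the expansion, 4 of 12 would be left out.

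**3. The texts side by side.**

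| Source | HI in the lead-in |
|---|---|
| Protocol Summary, Study Assessments | all patients |
| Protocol 2.2 | listed, no disease limit |
| Protocol 7.7.1 | IWG criteria for all patients |
| Protocol 9.3.6 | listed for the lead-in |
| SAP Appendix 2 footnote | oligoblastic AML and CMML also covered |
| SAP 8.2.2.1.2 | MDS only |

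SAP 8.2.2.1.2 is the clear outlier. The Appendix 2 footnotes do not name erythroleukemia, so for that patient the case rests on the protocol Summary and 7.7.1.

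**4. What the open denominator can do.** No HI counts are given, so the counts here are assumptions. Let x be the number of MDS responders and k the number of non-MDS responders (0 to 5).

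- MDS only, denominator 7: x/7
- MDS only, denominator 12: x/12
- Protocol: (x + k)/12

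With x = 3 the first gives 42.9% (exact 95% CI 9.9% to 81.6%) and the second 25.0% (5.5% to 57.2%). For any x above zero the first exceeds the second by a factor of 12/7 = 1.71. The gap runs from 0 points at x = 0 to 100.0 − 58.3 = 41.7 points at x = 7. The protocol's estimate with x = 3 runs from 3/12 = 25.0% (k = 0) to 8/12 = 66.7% (k = 5), so the restriction could move the estimate either way. Whatever the outcome, the widest possible exact 95% CI is 0.717 with 7 patients and 0.578 with 12.

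**5. Whether the data exist.** The protocol's lead-in schedule (Table 1, footnote 5) required blood counts twice during screening at least a week apart, which matches the HI baseline rule in Appendix 2. Footnote 22 required transfusion history and on-treatment transfusions. Neither is limited by disease.

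**6. Confirmation.** SAP 6.1.1 ties the note to MDS patients. But 8.2.2.1.1 requires confirmation for the lead-in response rate without a disease limit, as protocol 9.3.2 does. SAP Appendix 2, to which 6.1.1 itself refers, requires CR and PR to last at least 4 weeks. The only explicit exemption, in SAP 8.2.1, is for the expansion AML cohort.

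**The case against.** The strongest reply is that the protocol lets the SAP differ. Section 9 says the SAP may modify protocol plans, and only major changes to the primary endpoint or its analysis need an amendment. HI in the lead-in is secondary and descriptive, so a narrower population would be permissible. That stands as a matter of authority. It does not explain why the change is unlisted, why it conflicts with the SAP's own Appendix 2 footnote, or what the denominator is.

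Second, the SAP has a default denominator: the full analysis set (5.1, 8.1), with patients not known to have responded counted as non-responders (7.2). This favors 12 but does not settle how the disease limit interacts with it.

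Third, SAP 6.1.2.1.2 is weak evidence. It sits under MDS Cohort and follows a section headed AML Cohort, which are the names of the expansion cohorts. Read that way it agrees with the protocol. This is accepted: the firm conflict is the parenthesis in 8.2.2.1.2.

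A reader might also infer from SAP 6.1.1 that non-MDS lead-in responses would count without confirmation, and that the lead-in response rate is therefore exposed, since 3 of the 4 preliminary CRs were in AML patients (protocol 1.2.13.2). The documents do not support this. The governing section, 8.2.2.1.1, requires confirmation for the lead-in response rate, and 6.1.1 does not say that anyone in the lead-in is exempt. A fall from 4/12 = 33% to 1/12 = 8% would need all three AML CRs to fail confirmation, which nothing in the documents suggests. The 4 also includes a CR reached after the data cutoff.

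**Conclusion.** The point holds for HI. SAP 8.2.2.1.2 contradicts the protocol and the SAP's own Appendix 2, leaves 5 of 12 lead-in patients out of a stated secondary endpoint, and does not settle whether the denominator is 7 or 12. The count of 5 rests on the disease mix in the documents, with CMML kept separate from MDS. The 43% and 25% are illustrations from an assumed 3 responders and say nothing about the actual HI rate.

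The confirmation note in SAP 6.1.1 is loose wording only. It would be wrong to conclude that the 5 patients are scored under different rules for both HI and response rate.

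The consequence is small. The lead-in is complete, its primary endpoint is safety, HI enters no decision rule, and the expansion's primary CR endpoint is untouched. This is a desirable correction, not one on which the trial's conclusions depend.

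**What to change.** - **SAP 8.2.2.1.2:** delete the MDS restriction. Report HI on all 12 lead-in patients in the full analysis set, with the 7 MDS patients as a subset row and both denominators stated.
- **SAP 6.1.2.1.2:** say that the MDS limit on HI applies to the expansion.
- **SAP 6.1.1, Response Rate (alignment only):** make the confirmation note cover all lead-in patients and, in the expansion, MDS patients, in line with SAP 8.2.2.1.1 and protocol 3.3.2.

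If the sponsor does intend to restrict lead-in HI to MDS, the SAP should list this as a change, give the reason, state the denominator and reconcile the Appendix 2 footnote.

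The cost is a few words in the SAP and one table shell. The protocol already called for the blood counts and transfusion records, so no new data are needed.
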